Inclusion Criteria (Expansion Part B [Randomized H2H])	
Each potential subject must fulfill all of the following criteria to be eligible for inclusion in the Expansion Part B of the trial:
 

• Must be at least 18 years of age.

• Must sign an ICF prior to any Screening procedures. Where required by local or country specific regulations, each subject must sign a separate ICF if he or she agrees to provide samples for genomic biomarker analysis (DNA and RNA).

• ECOG PS score 0, 1, or 2.

• Must have fresh bone marrow samples collected at Screening.

• Has acceptable laboratory test results during the Screening period, as follows:

 

Parameter	Result	

a.	Creatinine clearance (CrCl) or serum creatinine	CrCl <math>\geq 20</math> mL/min (Cockcroft-Gault formula or EGFR (MDRD) or CKD-epi)	

aCZ	Creatinine clearance	See requirements per local health authorities	

b.	Serum alanine aminotransferase (ALT)	<math>\leq 2.5 \times \text{ULN}</math>	

c.	Serum aspartate aminotransferase (AST)	<math>\leq 2.5 \times \text{ULN}</math>	

d.	Total bilirubin	<math>\leq 2 \times \text{ULN}</math>, except in subjects with congenital bilirubinemia, such as Gilbert syndrome (direct bilirubin <math>\leq 2.0 \times \text{ULN}</math>)	

e.	Hemoglobin	<math>\geq 7.5</math> g/dL (<math>\geq 4.65</math> mmol/L) Note: Red blood cell transfusions are not permitted within 7 days before the laboratory test for eligibility review; recombinant human erythropoietin use is permitted	

f.	Absolute neutrophil count	<math>>1.0 \times 10^9/\text{L}</math> (<math>>1,000/\mu\text{L}</math>) Note: (Granulocyte colony stimulating factor [GCSF] use is permitted)	

g.	Platelet count	<math>>50 \times 10^9/\text{L}</math> (<math>>50,000/\mu\text{L}</math>) if bone marrow is <math>>50\%</math> involved in myeloma. Otherwise <math>\geq 75 \times 10^9/\text{L}</math> Note: Platelet transfusions are not permitted within 7 days before the laboratory test for eligibility review	

h.	Coagulation Status: Prothrombin time (PT), International normalized ratio (INR).	PT/INR/aPTT <math>\leq 1.5 \times \text{ULN}</math>	

	Parameter		Result	a.	Creatinine clearance (CrCl) or serum creatinine	CrCl $\geq 20$ mL/min (Cockcroft-Gault formula or EGFR (MDRD) or CKD-epi)	aCZ	Creatinine clearance	See requirements per local health authorities	b.	Serum alanine aminotransferase (ALT)	$\leq 2.5 \times \text{ULN}$	c.	Serum aspartate aminotransferase (AST)	$\leq 2.5 \times \text{ULN}$	d.	Total bilirubin	$\leq 2 \times \text{ULN}$ , except in subjects with congenital bilirubinemia, such as Gilbert syndrome (direct bilirubin $\leq 2.0 \times \text{ULN}$ )	e.	Hemoglobin	$\geq 7.5$ g/dL ( $\geq 4.65$ mmol/L) Note: Red blood cell transfusions are not permitted within 7 days before the laboratory test for eligibility review; recombinant human erythropoietin use is permitted	f.	Absolute neutrophil count	$>1.0 \times 10^9/\text{L}$ ( $>1,000/\mu\text{L}$ ) Note: (Granulocyte colony stimulating factor [GCSF] use is permitted)	g.	Platelet count	$>50 \times 10^9/\text{L}$ ( $>50,000/\mu\text{L}$ ) if bone marrow is $>50\%$ involved in myeloma. Otherwise $\geq 75 \times 10^9/\text{L}$ Note: Platelet transfusions are not permitted within 7 days before the laboratory test for eligibility review	h.	Coagulation Status: Prothrombin time (PT), International normalized ratio (INR).	PT/INR/aPTT $\leq 1.5 \times \text{ULN}$
Parameter		Result																													
a.	Creatinine clearance (CrCl) or serum creatinine	CrCl $\geq 20$ mL/min (Cockcroft-Gault formula or EGFR (MDRD) or CKD-epi)																													
aCZ	Creatinine clearance	See requirements per local health authorities																													
b.	Serum alanine aminotransferase (ALT)	$\leq 2.5 \times \text{ULN}$																													
c.	Serum aspartate aminotransferase (AST)	$\leq 2.5 \times \text{ULN}$																													
d.	Total bilirubin	$\leq 2 \times \text{ULN}$ , except in subjects with congenital bilirubinemia, such as Gilbert syndrome (direct bilirubin $\leq 2.0 \times \text{ULN}$ )																													
e.	Hemoglobin	$\geq 7.5$ g/dL ( $\geq 4.65$ mmol/L) Note: Red blood cell transfusions are not permitted within 7 days before the laboratory test for eligibility review; recombinant human erythropoietin use is permitted																													
f.	Absolute neutrophil count	$>1.0 \times 10^9/\text{L}$ ( $>1,000/\mu\text{L}$ ) Note: (Granulocyte colony stimulating factor [GCSF] use is permitted)																													
g.	Platelet count	$>50 \times 10^9/\text{L}$ ( $>50,000/\mu\text{L}$ ) if bone marrow is $>50\%$ involved in myeloma. Otherwise $\geq 75 \times 10^9/\text{L}$ Note: Platelet transfusions are not permitted within 7 days before the laboratory test for eligibility review																													
h.	Coagulation Status: Prothrombin time (PT), International normalized ratio (INR).	PT/INR/aPTT $\leq 1.5 \times \text{ULN}$																													

		activated partial thromboplastin time (aPTT)	
	

• A woman of reproductive potential must agree to use adequate contraception during the trial and for 12 months after the last GEN3014 IV or daratumumab SC administration. Adequate contraception is defined as highly effective methods of contraception. In countries where 2 highly effective methods of contraception are required, both methods will be required for inclusion.

• A woman of childbearing potential must have a negative serum <math>\beta</math>-hCG at Screening and within 72 hours of the first dose of study treatment prior to dosing.

• A woman must agree not to donate eggs (ova, oocytes) for the purposes of assisted reproduction during the trial and for 12 months after receiving the last dose of GEN3014 IV or daratumumab SC.

• A man who is sexually active with a woman of childbearing potential and has not had a vasectomy must agree to use a barrier method of birth control, eg, either condom with spermicidal foam/gel/film/cream/suppository or partner with occlusive cap (diaphragm or cervical/vault caps) with spermicidal foam/gel/film/cream/suppository, and all men must also not donate sperm during the trial and for 12 months after receiving the last dose of GEN3014 IV or daratumumab SC.

• Must have documented multiple myeloma as defined by the criteria below and have evidence of disease progression on the most recent prior treatment regimen based on IMWG criteria:

○ Prior documentation of monoclonal plasma cells in the bone marrow <math>\geq 10\%</math> or presence of a biopsy-proven plasmacytoma.

 
and
 

○ Measurable disease at baseline as defined by any of the following:

▪ IgG, IgA, IgD, or IgM myeloma: Serum M-protein level <math>\geq 0.5</math> g/dL (<math>\geq 5</math> g/L) or urine M-protein level <math>\geq 200</math> mg/24 hours;

 
or
 

▪ Light chain myeloma: Serum Ig FLC <math>\geq 10</math> mg/dL and abnormal serum Ig kappa lambda FLC ratio.

 

• Subject received at least 3 prior lines of therapy including a PI and an IMiD in any order, or who is double refractory to a PI and an IMiD; or subject received at least 2 prior lines of therapy if 1 of those lines included a combination of PI and IMiD. Note: Subjects should not have received any anti-CD38 antibody (eg, daratumumab, isatuximab). Anti-CD38 mAb-naïve RRMM subjects will be enrolled from ex-US countries.

• Potassium level <math>\geq 3.0</math> mEq/L (<math>\geq 3.0</math> mmol/L); and corrected serum calcium <math>\leq 14.0</math> mg/dL (<math>\leq 3.5</math> mmol/L) or free ionized calcium <math>\leq 6.5</math> mg/dL (<math>\leq 1.6</math> mmol/L).

		
Exclusion Criteria (Dose Escalation and Expansion Part A [GEN3014 Single Cohorts])	
Any potential subject who meets any of the following criteria will be excluded from being treated in the Dose Escalation and/or Expansion Part A (GEN3014 Single Cohorts) of the trial.
 

• Prior treatment with any anti-CD38- directed therapies (eg, daratumumab, isatuximab, CD38 CAR-T, bispecific Ab) in anti-CD38 mAb-naïve RRMM Cohort. Note: Prior daratumumab or isatuximab exposure is allowed for anti-CD38 mAb-treated RRMM subjects in the Dose Escalation and anti-CD38 mAb-refractory RRMM Cohort in the Expansion Part A.

• Treatment with an anti-cancer agent (eg, small molecule, antibody, chimeric antigen receptor T cell [CAR-T] cell therapy), chemotherapy, radiation therapy, or major surgery within 2 weeks prior to the first dose of GEN3014. Note different timeframe requirements per local health authorities.

		

	
 
• Treatment with an investigational drug within 4 weeks or 5 half-lives, whichever is shorter, prior to the first dose of GEN3014.
 
• Cumulative dose of corticosteroids more than the equivalent of <math>\geq 140</math> mg of prednisone within 2-week period before the first dose of GEN3014.
 
• Has clinically significant cardiac disease, including: 
 
○ Myocardial infarction within 1 year prior to the first dose of GEN3014, or unstable or uncontrolled disease/condition related to or affecting cardiac function (eg, unstable angina, congestive heart failure, New York Heart Association Class III-IV) uncontrolled cardiac arrhythmia (CTCAE v5.0 grade 2 or higher) or clinically significant ECG abnormalities.
 
○ Screening 12-lead ECG showing a baseline QT interval as corrected by Fridericia's formula (QTcF) <math>>480</math> msec.
 
○ Refer to requirements for subjects from the US per local health authorities.
 
 
 
• Toxicities from previous anti-cancer therapies have not resolved to baseline levels or to Grade 1 or less except for alopecia and peripheral neuropathy.
 
• Primary central nervous system (CNS) tumor or known CNS involvement at Screening.
 
• Has known history/positive serology for hepatitis B (unless immune due to vaccination or unless passive immunization due to Ig therapy): 
 
○ Positive test for antibodies to the hepatitis B core antigen (anti-HBc)
 
 
and
 
 
○ Negative test for antibodies to the hepatitis B surface antigen (anti-HBs).
 
 
 
• Known medical history or ongoing hepatitis C infection that has not been cured.
 
• Known history of seropositivity of human immunodeficiency virus (HIV).
 
• Currently receiving any other investigational agents.
 
• A woman who is pregnant or breast-feeding, or who is planning to become pregnant while enrolled in this trial or within 12 months after the last dose of GEN3014.
 
• A man who plans to father a child while enrolled in this trial or within 12 months after the last dose of GEN3014.
 
 
Specific Exclusion Criteria for RRMM:
 
 
• Prior allogeneic HSCT.
 
• Autologous HSCT within 3 months of the first dose of GEN3014.
 
 
Specific Exclusion Criteria for R/R AML:
 
 
• <math><5\%</math> blasts in blood or bone marrow at Screening.
 
• WBC counts <math>\geq 50,000/\mu\text{L}</math> in peripheral blood that cannot be controlled by hydroxyurea prior to the first dose of GEN3014.
 
• Prior autologous HSCT.
 
• Allogeneic HSCT within 3 months of the first dose of GEN3014.
 
• Active graft-versus-host-disease requiring immunosuppressive treatment. Any immunosuppressive medication (eg, calcineurin inhibitors) must be stopped <math>\geq 4</math> weeks prior to the first dose of GEN3014.
 
 
Additional Exclusion Criteria for All Subjects:
 
 
• History of allergic reactions attributed to compounds of similar active substance or excipients.
 
• Has known past (within 3 years) or current malignancy other than inclusion diagnosis, except for:
 

--	---

	
 
a. Cervical carcinoma of Stage 1B or less.
 
b. Non-invasive basal cell or squamous cell skin carcinoma.
 
c. Non-invasive, superficial bladder cancer.
 
d. Prostate cancer with a current PSA level <0.1 ng/mL.
 
e. Any curable cancer with a CR of >2 years duration.
 
 
 
• Prior treatment with live, attenuated vaccines within 28 days prior to initiation of trial drug. Examples of live vaccines include, but are not limited to, the following: measles, mumps, rubella, varicella/zoster (chicken pox), yellow fever, rabies, Bacillus Calmette–Guérin, and typhoid vaccine. Seasonal influenza vaccines for injection are generally killed virus vaccines and are allowed; however, intranasal influenza vaccines (eg, FluMist®) are live attenuated vaccines and are not allowed. Experimental and/or nonauthorized severe acute respiratory syndrome coronavirus 2 (SARS-CoV-2) vaccinations are not allowed.
 
 
Additional Exclusion Criterion for RRMM:
 
 
• Known allergies, hypersensitivity, or intolerance to mAbs, human proteins, hyaluronidase, or excipients (refer to GEN3014 IB and daratumumab IB).
 

Exclusion Criteria (Expansion Part B [Randomized H2H])	
Any potential subject who meets any of the following criteria will be excluded from being treated in the Expansion Part B (Randomized H2H) of the trial.
 
 
• Prior or concurrent treatment with any CD38-directed therapies (eg, daratumumab, isatuximab, CD38 CAR-T, bispecific Ab) for RRMM.
 
• Treatment with an anti-cancer agent (eg, small molecule, antibody, CAR-T cell therapy), chemotherapy, radiation therapy, or major surgery within 2 weeks prior to randomization. Note different timeframe requirements as per local health authorities.
 
• Treatment with an investigational drug (including anti-cancer investigational vaccines) within 4 weeks or 5 half-lives, whichever is shorter, prior to the randomization.
 
• Radiation therapy for treatment of plasmacytoma within 14 days of randomization (palliative radiation for pain control secondary to lytic lesion is allowed).
 
• A maximum cumulative dose of dexamethasone 160 mg within 28 days of randomization.
 
• Has clinically significant cardiac disease, including: 
 
○ Myocardial infarction within 6 months before the date of randomization, or unstable or uncontrolled disease/condition related to or affecting cardiac function (eg, unstable angina, congestive heart failure, New York Heart Association Class III-IV uncontrolled cardiac arrhythmia (CTCAE v5.0 grade 2 or higher), or clinically significant electrocardiogram (ECG) abnormalities.
 
○ Screening 12-lead ECG showing a baseline QT interval as corrected by Fridericia's formula (QTcF) >480 msec.
 
○ Refer to requirements for subjects from the US per local health authorities.
 
 
 
• Toxicities from previous anti-cancer therapies have not resolved to baseline levels or to Grade 1 or less except for alopecia and peripheral neuropathy.
 
• Primary central nervous system (CNS) tumor, current or history of CNS involvement by the disease under investigation.
 
• Has known history/positive serology for hepatitis B (unless immune due to vaccination or unless passive immunization due to Ig therapy): 
 
○ Positive test for antibodies to the hepatitis B core antigen (anti-HBc)
 
and
 
○ Negative test for antibodies to the hepatitis B surface antigen (anti-HBs).
 
 
 

	
 
• Known to be seropositive for hepatitis C (except in the setting of a sustained virologic response [SVR], defined as aviremia at least 12 weeks after completion of antiviral therapy).
 
• Known to be positive for human immunodeficiency virus (HIV), with 1 or more of the following: 
 
a. Not receiving highly active antiretroviral therapy (ART)
 
b. Had a change in ART within 6 months of the start of Screening
 
c. Receiving ART that may interfere with trial treatment (consult sponsor for review of medication prior to enrollment)
 
d. CD4 count <350 cells/mm^3 at Screening
 
e. Acquired immunodeficiency syndrome-defining opportunistic infection within 6 months of start of Screening
 
f. Not agreeing to start ART and be on ART >4 weeks plus having HIV viral load <400 copies/mL at end of 4-week period (to ensure ART is tolerated and HIV controlled).
 
 
 
• Pulmonary 
 
a. COPD with a FEV1 <50% of predicted normal. Note that FEV1 testing is required for subjects suspected of having COPD and subjects must be excluded if FEV1 is <50% of predicted normal.
 
b. Moderate or severe persistent asthma within the past 2 years, or uncontrolled asthma of any classification. Note that subjects who currently have controlled intermittent asthma or controlled mild persistent asthma are allowed to participate in the trial.
 
 
 
• Contraindications or life-threatening allergies, hypersensitivity, or intolerance to monoclonal antibodies, hyaluronidase, human proteins, or their excipients (refer to daratumumab IB), or known sensitivity to mammalian-derived products.
 
• Prior treatment with live, attenuated vaccines within 28 days prior to initiation of trial drug. Examples of live vaccines include, but are not limited to, the following: measles, mumps, rubella, varicella/zoster (chicken pox), yellow fever, rabies, Bacillus Calmette–Guérin, and typhoid vaccine. Seasonal influenza vaccines for injection are generally killed virus vaccines and are allowed; however, intranasal influenza vaccines (eg, FluMist®) are live attenuated vaccines and are not allowed. Experimental and/or nonauthorized severe acute respiratory syndrome coronavirus 2 (SARS-CoV-2) vaccinations are not allowed.
 
• Major surgery within 2 weeks before randomization, or will not have fully recovered from surgery, or has surgery planned during the time the subject is expected to participate in the trial. Note: subjects with planned surgical procedures to be conducted under local anesthesia may participate. Kyphoplasty or vertebroplasty are not considered major surgery. If there is a question about whether a procedure is considered a major surgical procedure, the investigator must consult with the sponsor and resolve any issues before enrolling a subject in the trial.
 
• Plasmapheresis within 28 days before randomization.
 
• Any concurrent medical or psychiatric condition or disease (eg, active systemic infection, uncontrolled diabetes, acute diffuse infiltrative pulmonary disease) that is likely to interfere with the trial procedures or results, or that in the opinion of the investigator, would constitute a hazard for participating in this trial.
 
• Known or suspected of not being able to comply with the study protocol (eg, because of alcoholism, drug dependency, or psychological disorder). Subject has any condition for which, in the opinion of the investigator, participation would not be in the best interest of the subject (eg, compromise the well-being) or that
 

--	---

[figure not shown]
	
could prevent, limit, or confound the protocol-specified assessments. Subject is taking any prohibited medications.
 
 
• Currently receiving any other investigational agents.
 
• A woman who is pregnant or breast-feeding, or who is planning to become pregnant while enrolled in this trial or within 12 months after the last dose of GEN3014 or daratumumab SC.
 
• A man who plans to father a child while enrolled in this trial or within 12 months after the last dose of GEN3014 or daratumumab SC.
 
• Prior allogeneic HSCT.
 
• Autologous HSCT within 3 months of the first dose of GEN3014 or daratumumab SC.
 
• Contraindications or life-threatening allergies, hypersensitivity, or intolerance to any trial treatment or its excipients, or any of its metabolites (refer to GEN3014 and daratumumab IBs).
 
• Active malignancies (ie, progressing or requiring treatment change in the last 24 months) other than the disease being treated under study. The only allowed exceptions are: 
 
a. non-invasive cervical cancer treated within the last 24 months that is considered completely cured.
 
b. skin cancer (non-melanoma or melanoma) treated within the last 24 months that is considered completely cured.
 
c. non-muscle invasive bladder cancer (NMIBC).
 
d. localized prostate cancer (N0M0). 
 
○ with a Gleason score of 6, treated within the last 24 months or untreated and under surveillance,
 
○ with a Gleason score of 3+4 that has been treated more than 6 months prior to full study screening and considered to have a very low risk of recurrence,
 
○ or history of localized prostate cancer and receiving androgen deprivation therapy and considered to have a very low risk of recurrence.
 
 
 
e. Breast cancer: 
 
○ adequately treated lobular carcinoma in situ or ductal carcinoma in situ,
 
○ or history of localized breast cancer and receiving antihormonal agents and considered to have a very low risk of recurrence.
 
 
 
f. Malignancy that is considered cured with minimal risk of recurrence.
 
 
 
 
NOTE: Investigators should ensure that all study enrollment criteria have been met at Screening. If a subject's status changes (including laboratory results or receipt of additional medical records) after Screening but before the first dose of trial treatment is given such that subject no longer meets all eligibility criteria, then the subject should be excluded from participation in the trial.

--	--

Trial drug	
GEN3014 will be administered intravenously and daratumumab will be administered subcutaneously (daratumumab SC).
 
Both GEN3014 and daratumumab SC will be administered in 4-week (ie, 28-day) cycles until disease progression, unacceptable toxicity, or withdrawal of consent: once every week (Q1W) in Cycles 1-2; every 2 weeks (Q2W) in Cycles 3-6; and every 4 weeks (Q4W) in Cycles 7 and beyond. The first dose of GEN3014 in Cycle 1 will be split into 2 doses and administered in 2 consecutive days.
 
Premedication (corticosteroids, antipyretics, antihistamines, a leukotriene receptor antagonist) and post-medication (corticosteroids) will be given to reduce the risk of infusion-related reactions (IRRs) and systemic administration-related reactions (sARRs).
 
In the Dose Escalation, GEN3014 will be tested at 6 DLs in RRMM with the first 2 DLs being single-subject followed by standard 3-subject DLs. Intrasubject dose escalation will be performed for the first RRMM cohort (MM-DL1). From MM-DL3 and onward (ie, DL 4, 8, 16, and 24 mg/kg), the initial DL size is 3 subjects.
 
In the Dose Escalation, CCI [REDACTED], with standard 3-subject cohorts. The R/R AML Cohort will be initiated after the trial has cleared the DL of 16 mg/kg in the RRMM Cohort with preliminary data on safety, PK, and pharmacodynamics in subjects with RRMM who have been treated with GEN3014 at DLs up to 16 mg/kg. DLs and the dosing schedule for the R/R AML Cohort may be modified based on emerging PK, pharmacodynamic, and safety data.
 
In the Expansion Part A, 3 cohorts of subjects (anti-CD38 mAb-naïve RRMM, anti-CD38 mAb-refractory RRMM, and R/R DLBCL) will be treated with GEN3014 at the RP2D identified for RRMM from the Dose Escalation and a fourth cohort of subjects with R/R AML will be treated with GEN3014 at the RP2D identified for AML from the Dose Escalation. If the preliminary efficacy and safety are judged to be favorable in the initial 10 anti-CD38 mAb-naïve subjects with RRMM who received 16 mg/kg or 24 mg/kg (in the Dose Escalation or Expansion Part A), approximately 80 subjects in the anti-CD38 mAb-naïve RRMM cohort will be randomized to receive either GEN3014 at the RP2D or daratumumab SC at 1800 mg.

Statistics	
Dose Escalation:
 
During dose escalations of GEN3014, by utilizing an mBOIN, recommendations will be provided to the DEC to either escalate, remain, or de-escalate next DL in the escalation part of the trial. The mBOIN aims to characterize the DLT rate at each DL such that the RP2D (and possibly the MTD) can be determined. Escalation data will be summarized by DL and indication (RRMM or R/R AML).
 
Expansion Part A
 
The Expansion Part A will be conducted in 4 parallel cohorts:
 
 
• Anti-CD38 mAb-naïve RRMM (N=approximately 10 subjects)
 
• Anti-CD38 mAb-refractory RRMM (N=20 subjects)
 
• R/R DLBCL (up to 40 subjects): Based on a Simon's 2-stage design, up to 40 subjects with R/R DLBCL may be treated with GEN3014. The initial stage consists of 20 subjects and if least 5 of 20 subjects respond to GEN3014, the futility bar is passed.
 
• R/R AML (N=20 subjects)
 
 
The response assessment for each disease indication, for the primary endpoint of ORR, will be:
 
 
• The International Myeloma Working Group consensus criteria (IWMG) 2016 for MM,
 
• The revised response criteria for Hodgkin and non-Hodgkin lymphoma (Lugano classification) for DLBCL, and
 
• The International Working Group (IWG) response criteria for AML.
 

	
The ORR for each expansion cohort will be presented with the exact 2-sided 95% confidence intervals (CI) (using the Clopper-Pearson method).
 
Expansion Part B (Randomized H2H)
 
After a 10-subject lead-in of GEN3014, an additional approximately 80-subject H2H comparison of GEN3014 IV vs daratumumab SC will be conducted among anti-CD38 mAb-naïve RRMM subjects. (The randomized H2H comparison will be conducted if at least 2 out of the 10 subjects respond to GEN3014.)
 
The ratio in ORR between the 2 arms in Expansion Part B will be described using the Miettinen-Nurminen method. The data will be evaluated by sponsor to guide further clinical development.
 
AEs will be described using summary statistics. Safety stopping guidance based on the rate of Grade <math>\geq 4</math> treatment-related AEs and treatment-related deaths is established for the expansion cohorts. Individual curves of serum concentration for GEN3014 will be presented for all subjects. PK parameters will be calculated based on non-compartmental methods and calculated separately.

GCP Compliance	
This trial will be conducted in compliance with the protocol, International Council for Harmonisation Good Clinical Practice, ICH GCP E6(R2), in compliance with the principles of the Declaration of Helsinki, and other applicable regulatory requirements.

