### 4.1.3 Expansion Part A (GEN3014 Single Cohorts)

In the Expansion Part A (GEN3014 Single Cohorts), there are 4 disease cohorts.

- Three cohorts of subjects will be treated with GEN3014 at the RP2D identified for RRMM from the Dose Escalation:
  - Anti-CD38 mAb-naïve RRMM (N=10 subjects). Data from the initial 10 response-evaluable subjects (defined in Section 9.3), inclusive of those anti-CD38 mAb-naïve subjects with RRMM who received GEN3014 at 16 mg/kg or 24 mg/kg from the Dose Escalation and/or from the Expansion Part A, will be reviewed by the Safety Committee and DMC when they have completed  $\geq 2$  cycles of treatment. If 2 or more (out of the initial 10) subjects respond to GEN3014, an H2H comparison to daratumumab SC will be initiated; see Sections 4.1.4 and 9.5.1. (Assessment of disease response will be conducted by the investigator in accordance with the IMWG 2016 Response Criteria.) The lead-in part may consist of more than 10 subjects to ensure exposure to at least 2 cycles of GEN3014 treatment.
  - Anti-CD38 mAb-refractory RRMM (N=20 subjects).
  - R/R DLBCL (N=up to 40 subjects). This cohort will include at least 15 R/R DLBCL subjects with  $>50\%$  CD38 expression. When the initial 20 response evaluable subjects have completed  $\geq 2$  cycles of GEN3014 treatment, an interim futility analysis will be conducted; see Section 9.5.2. Based upon the response at the interim futility analysis, an additional 20 subjects may be enrolled into this cohort for a total of 40 subjects.

See Sections 5.1.2 and 5.2.1 for inclusion and exclusion criteria.

- A fourth cohort of subjects with R/R AML (N=20 subjects) will be treated with GEN3014 at the RP2D identified for AML from the Dose Escalation. See Sections 5.1.2 and 5.2.1 for inclusion and exclusion criteria.

The administration schedule in Expansion Part A will be the same as in Dose Escalation (see Section 6.1.6.1).

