#### **4.3.2 Expansion Part A (GEN3014 Single Cohorts)**

The GEN3014 dose for Expansion Part A (GEN3014 Single Cohorts) subjects with anti-CD38 mAb-naïve RRMM, anti-CD38 mAb-refractory RRMM, and R/R DLBCL will be the RP2D which is based on assessment of all available data from the Dose Escalation part of this trial. The rationale to use the same RP2D for R/R DLBCL is based on the observation that the PK and safety profiles of daratumumab in B-NHL subjects including DLBCL are similar to MM subjects (Salles et al., 2019). Based on assessment of all available data from the Dose Escalation part of this trial, 16 mg/kg was selected as the RP2D.

Subjects with R/R AML will be treated with GEN3014 at the RP2D identified for R/R AML from the Dose Escalation.

The GEN3014 administration schedule is based upon the primary results of the daratumumab GEN501 and SIRIUS studies, and similar mechanism of action between GEN3014 and daratumumab (Usmani et al., 2020).

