## **6.1.6 Treatment Schedule**

### **6.1.6.1 GEN3014 Administration Schedule for Expansion Part A (GEN3014 Single Cohorts) and Expansion Part B (Randomized H2H)**

GEN3014 will be administered as an IV infusion at the RP2D (ie, 16 mg/kg) in cycles of 4 weeks, ie, 28 days, as follows:

- Cycle 1 (Q1W) on Days 1, 2\*, 8, 15, and 22. Note: \*The first dose of GEN3014 will be split into 2 consecutive days (ie, C1D1 and C1D2).
- Cycle 2 (Q1W) on Days 1, 8, 15, and 22
- Cycle 3-6 (Q2W) on Days 1 and 15
- Cycle 7 and beyond (Q4W) on Day 1

Dosing days may be adjusted to accommodate the schedule of the site or the subject. Changes to within-cycle dosing should not affect Day 1 of the next cycle.

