##### **8.4.3.2 Overdose/Medication Errors**

GEN3014 overdose is defined as a subject receiving a dose of the trial drug in excess of 10% of that specified in this protocol. All cases of overdose must be reported to the sponsor within 24 hours of knowledge of the event (see additional details in Section 8.5, Treatment of Overdose). In case of daratumumab SC overdose, please refer to the daratumumab IB for information. Overdose of concomitant medication should only be reported if associated with AEs whether serious or not.

Medication errors (including infusion rate errors) and uses outside what is foreseen in the protocol, including misuse and abuse of the product, should be reported within 24 hours of knowledge of the event.

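### Protocol Section 6.1.6.1 gives 16 mg/kg for all of Expansion Part A, while three other passages dose the R/R AML cohort at its own RP2D, and no visible text says the two are the same

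*Protocol*

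**What the plan says.** Three protocol passages tie the R/R AML expansion cohort to a dose found in the AML escalation.

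- Synopsis (Section 1.1, trial drug): "a fourth cohort of subjects with R/R AML will be treated with GEN3014 at the RP2D identified for AML from the Dose Escalation". The other three Part A cohorts, two in RRMM and one in R/R DLBCL, are assigned the RRMM RP2D instead.
- Section 4.1.3: the AML cohort (N=20) "will be treated with GEN3014 at the RP2D identified for AML from the Dose Escalation".
- Section 4.3.2: "Subjects with R/R AML will be treated with GEN3014 at the RP2D identified for R/R AML from the Dose Escalation".

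None of the three gives a mg/kg figure for AML. Section 4.3.2 does give one for the other cohorts: the paragraph on the two RRMM cohorts and R/R DLBCL ends by stating that "16 mg/kg was selected as the RP2D". AML follows in a sentence of its own.

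Section 6.1.6.1 sets out GEN3014 administration under a heading that names Expansion Part A and Expansion Part B. It says that "GEN3014 will be administered as an IV infusion at the RP2D (ie, 16 mg/kg) in cycles of 4 weeks". It does not separate AML from the other cohorts.

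**The concern.** R/R AML is one of the four Part A cohorts, so Section 6.1.6.1 applies to it as written. That section speaks of a single RP2D and puts a number on it. The number is introduced elsewhere only for RRMM and DLBCL, while the cohort-specific passages send AML to a dose selected from AML data.

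A site that follows Section 6.1.6.1 would give 16 mg/kg whatever the AML escalation had selected. A site that follows Section 4.1.3 would give the AML RP2D. If these are different doses, the cohort's primary ORR might not describe the dose that the plan says it describes. The dose that defines an overdose would also be unclear. Section 6.6.2 allows no dose increase or decrease in Part A, so an investigator has no room to settle the matter locally.

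**Working it through.** The check is mainly a comparison of passages. The plan states no figure here that needs to be reproduced.

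**1. Is AML within the scope of Section 6.1.6.1?** Yes. Section 6.4.2.2 lists R/R AML among the four Part A cohorts, and the section heading covers Part A without restriction. Section 4.1.3 also refers the reader to Section 6.1.6.1 for the Part A administration schedule, directly after its AML item.

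**2. Is the AML RP2D a separate determination?** Yes.

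| Feature | RRMM | R/R AML | Source |
|---|---|---|---|
| Basis for RP2D | toxicity seen in RRMM | toxicity seen in AML | Section 4.1 |
| Target DLT rate | 30% | 25% | Section 4.1.2 |
| Decision table | Table 4-3 | Table 4-4 | Section 4.1.2 |
| Planned dose levels | 6 | 3 | Section 4.1.1 |

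**3. Does another visible passage give the AML expansion dose or equate the two?** No. The Part A AML schedule (Table 1-6) describes the split first dose and the later full doses without mg/kg. Its administration row refers to the Dose Escalation sections. Section 4.3.3 and Section 6.6.3.1 also give 16 mg/kg, but both concern Part B, so they neither add to the conflict nor resolve it. Section 4.1.2.5 says that the committees will try to align the RP2Ds. That is an aim and does not report a result.

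**4. When would the overdose rule be affected?** Section 8.4.3.2 states that "GEN3014 overdose is defined as a subject receiving a dose of the trial drug in excess of 10% of that specified in this protocol". Let D be the AML RP2D in mg/kg, which is not visible.

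- If 16 mg/kg is the specified dose, a subject given D exceeds the limit when D > 1.10 × 16 = 17.6 mg/kg.
- If D is the specified dose, a subject given 16 mg/kg exceeds the limit when 16 > 1.10 × D, that is, when D < 16 / 1.10 = 14.5 mg/kg (rounded).
- If D lies between about 14.5 and 17.6 mg/kg, neither reading makes the other dose an overdose. The instructions still disagree unless D = 16.

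These are conditional limits. They say nothing about what D is.

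**The case against.** The strongest reply is that no numeric contradiction has been shown. The AML dose levels and most of the AML dose rationale are redacted, and redaction is not a fault in the plan. Section 4.1.2.5 states the aim of aligning the RP2Ds, so Section 6.1.6.1 could be recording one aligned RP2D for all of Part A. In addition, the reference from Section 4.1.3 to Section 6.1.6.1 is to the schedule and not to the dose level. Section 4.4.1.2 gives individual trial durations in Part A for RRMM and DLBCL but not for AML, so it is uncertain how many AML expansion subjects will be dosed under this text.

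Much of this stands, and it limits the point. A reader might infer that AML subjects will be dosed at a level different from the one selected for them, or might put a ratio on the gap by borrowing the RRMM dose ladder. The documents support neither: the AML levels cannot be seen, and nothing visible says that they follow the RRMM ladder.

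What does not stand is that the text is therefore consistent. Reading Section 6.1.6.1 as a record of alignment requires a step that no visible passage takes. The sentences that disagree are themselves unredacted. The missing AML durations do not remove the cohort, which remains in the synopsis, Sections 4.1.3 and 6.4.2.2, and the stopping guidance in Table 9-5.

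**Conclusion.** The protocol has an unreconciled dose statement for the R/R AML expansion cohort. Section 6.1.6.1 is the outlier: the synopsis and Sections 4.1.3 and 4.3.2 agree with one another. It would be wrong to describe this as the synopsis contradicting the body of the protocol.

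The point covers one cohort with a planned size of 20. Its consequences are conditional. If the AML RP2D is 16 mg/kg, the texts coincide and the only gap is that nobody has said so. If it is not, sites have two conflicting instructions, and the overdose reference in Section 8.4.3.2 is ambiguous for that cohort.

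A reader might also infer that planned dose intensity is undefined in the SAP. It is not: SAP Section 5.5.1.2 is written in terms of a generic dose level and works for whatever dose is assigned.

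The conclusion rests on the visible text only. It assumes that no redacted passage states the AML RP2D for expansion. It takes no position on which dose is right.

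**What to change.** The sponsor should reconcile Section 6.1.6.1 with the synopsis and Sections 4.1.3 and 4.3.2, so that a single dose statement applies to the R/R AML expansion cohort. The same statement should serve as the reference dose for the overdose definition in Section 8.4.3.2. If the AML RP2D has been set equal to the RRMM one, a sentence saying so would be enough. If it has not, the passages need to be brought into agreement in whichever way the sponsor decides.

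The cost is a small change of protocol wording, made as a clarification or in the next amendment. It is best done before any AML expansion subject is dosed under the present text. No analysis, sample size or SAP text needs to change.
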